## 9 CLINICAL MONITORING

Clinical site monitoring is conducted to ensure that the rights and well-being of human subjects are protected, that the reported trial data are accurate, complete, and verifiable, and that the conduct of the trial is in compliance with the currently approved protocol/amendment(s), with GCP, and with applicable regulatory requirement(s).

- Monitoring for this study will be performed by the study CRO in accordance with the Clinical Monitoring Plan (CMP).
- A mix of on-site and centralized risk-based monitoring will be performed to ensure the safety of clinical subjects and the accuracy and completeness of study data.
- The sponsor will be provided with copies of monitoring reports per the timelines specified within the CMP.
- Details of clinical site monitoring tasks and scope are documented in the study's CMP. The CMP describes in detail who will conduct monitoring, at what frequency monitoring will be done, at what level of detail monitoring will be performed, and the distribution of monitoring reports.
- Independent audits may be conducted by the sponsor in accordance with the Clinical Quality Oversight Plan to ensure monitoring practices are performed consistently across all participating sites and that monitors are following the CMP.

## 10 STATISTICAL CONSIDERATIONS

### 10.1 STATISTICAL DESIGN MODEL AND ANALYTICAL PLANS

The therapeutic effect of the treatment will be investigated in one single group of subjects, with no control group. The observed mean effect will be compared with 0 as reference value. Overall baseline and demographic data will be summarized using descriptive statistics.

Subject disposition (e.g., the number of subjects enrolled, completed, and discontinued) will be summarized and medical history data will be listed. Prior and concomitant medications taken from screening and during the study will be categorized by World Health Organization (WHO) classification for therapeutic class and drug name, listed and summarized by number and percentage of subjects.

Final analyses are not limited to the summaries described herein. Analytical details and assumptions will be fully presented in the SAP.

### 10.2 STATISTICAL HYPOTHESES

The null and alternative hypothesis for change from baseline in BCVA letter score as measured by ETDRS testing method are:

$H_0$ : Change from baseline in BCVA letter score = 0

$H_1$ : Change from baseline in BCVA letter score  $\neq$  0 with  $\alpha_1 = 0.20$

### 10.3 ANALYSIS DATASETS

Four analysis datasets are possible; however, analyses may not necessarily be conducted with all four:

- **Intention-to-Treat (ITT) Dataset:** all enrolled subjects
- **Safety Dataset:** all subjects who received at least 1 dose of the study agent
- **Evaluable Dataset:** all subjects who complete at least 3 weeks of treatment during the 6-week treatment period
- **Per Protocol Dataset:** a subset of the Evaluable Dataset comprised of subjects who have no major protocol violations

The presentation of baseline characteristics will be based on the ITT dataset. All safety analyses will be performed for the Safety Dataset. Analyses of the primary and exploratory endpoints will focus on the Evaluable and/or Per Protocol Datasets.

## 10.4 PLANNED ANALYSES

### 10.4.1 ANALYSIS OF THE PRIMARY ENDPOINT

The therapeutic effect of the treatment will be investigated in one single group of subjects, with no control group. The changes from baseline in BCVA will be compared with 0 as reference value. The study is not designed to detect significant changes in BCVA over time. However, using available data, including changes in BCVA from baseline, descriptive summarization will be developed. Of particular interest will be the within-subject changes in BCVA from baseline and their distribution around a null value of zero.

### 10.4.2 ANALYSIS OF THE SECONDARY ENPOINT

Safety will be assessed for the following endpoints:

- Incidence, seriousness, and severity of adverse events
- Changes from baseline in clinical laboratory values
- Changes from baseline in physical examination
- Changes from baseline in vital signs

All treated subjects (i.e., all subjects who received at least 1 dose of the study agent) will be included in the safety evaluation. Safety analyses will be descriptive in nature and will be based on accepted standards.

Tabulations of frequencies/proportions will be used for the evaluation of categorical (qualitative) data, and tabulations of descriptive statistics will be used to evaluate continuous (quantitative) data.

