**7.2.2 SAFETY LABORATORY EVALUATIONS**

Blood samples and urine must be collected at every visit. Safety laboratory examinations will include hematology, biochemistry, coagulation and qualitative urine analysis.

- Hematology: hemoglobin, red blood cell count (RBC), white blood cell count (WBC) with differential, platelets
- Biochemistry: glucose, sodium, potassium, calcium, inorganic phosphate, creatinine, aspartate aminotransferase (AST), alanine aminotransferase (ALT), alkaline phosphatase (AP), lactate dehydrogenase (LDH), total bilirubin (if elevated provide direct bilirubin), urea, total protein, albumin, uric acid
- Coagulation: activated partial thromboplastin time (aPTT), prothrombin time (PT)/international normalized ratio (INR)
- Urine: potential of hydrogen (pH), glucose, erythrocytes, leukocytes, protein, nitrite

Glomerular filtration rate (GFR) will be estimated by the Cockcroft Gault Formula utilizing serum creatinine (see [Section 17.5](#)). All safety laboratory measurements will be performed by a central laboratory. Investigators will get guidance and instructions on laboratory sampling and processing through a separate Lab Manual provided by the central laboratory.

The investigator is responsible for determining and documenting if out of range laboratory values are clinically significant or not. All clinically significant values will be recorded as AEs in the eCRF and followed until resolution. Once resolved, the appropriate eCRF page(s) will be updated.

---

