The Kenward-Roger method will be used to determine denominator degrees of freedom. An unstructured variance-covariance matrix will be used for the above repeated measures model. If the model does not converge using the unstructured matrix, the first order autoregressive structure and the compound symmetry structure will be employed, in that order.

The above analyses will be repeated on the PP set as a sensitivity analysis.

Additionally, the number of subjects with change from baseline in BCVA letter score for the following categories will be summarized with counts and percentages:

- ≥ 15 letters;
- ≥ 14 and ≥ 10 letters;
- ≥ 9 and ≥ 5 letters;
- ≥ 4 and ≥ -4 letters;
- ≥ -5 and ≥ -9 letters;
- ≥ -10 and ≥ -14 letters;
- ≤ -15 letters.

BCVA results will also be presented in a data listing. BCVA results in the fellow eye are not included in the analyses but will be included in the listings. BCVA will also be summarized by visit using box plots.

15. Analysis of the Secondary Endpoints

The analyses for secondary endpoints (incidence, seriousness and severity of AEs) will be discussed in the next section as part of the safety analyses. There is no secondary efficacy endpoint for the study.

16. Safety Analyses

Safety will be assessed for the following endpoints using the Safety set:

- Incidence, seriousness, and severity of AEs;
- Observed slit-lamp biomicroscopy values;
- Observed intraocular pressure (IOP) values;
- Changes from baseline in clinical laboratory values;
- Changes from baseline in physical examination;
- Changes from baseline in vital signs.

Adverse events will be presented using frequencies and percentages of subjects.

Other safety endpoints including slit-lamp biomicroscopy, IOP, clinical laboratory values, physical examination, and vital signs will be summarized using descriptive statistics. Changes or shifts from baseline will also be summarized where appropriate. Assessments performed by eye (study eye and fellow eye) will be summarized separately. No statistical inferential testing will be performed for safety variables.

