16.4 Clinical Laboratory Values

Blood samples and urine must be collected at every visit. Safety laboratory examinations will include hematology, biochemistry, coagulation, and qualitative urine analysis.

- Serology (screening only): hepatitis A (anti-immunoglobulin M (IgM), anti-IGM)), hepatitis B (hepatitis B antigen, anti-HBs, DNA), hepatitis C (anti-hepatitis C virus (HCV), ribonucleic acid (RNA) if anti-HCV positive), hepatitis D (anti-IgM, anti-immunoglobulin G (IgG)), hepatitis E (anti-hepatitis E virus (HEV), anti-HEV IgM, RNA if anti-HEV IgM positive), anti-smooth muscle antibody (titer), anti-nuclear antibody (titer), anti-liver-kidney microsomes (LKM) antibody, antimitochondrial antibody, Epstein Barr virus (vascularized composite allotransplantation (VCA) IgG, VCA IgM), cytomegalovirus (IgG, IgM), herpes simplex virus (IgG, IgM), varicella (IgG, IgM), parvovirus (IgG, IgM), toxoplasmosis (IgG, IgM)
- Hematology: hemoglobin, red blood cell count (RBC), white blood cell count (WBC) with differential, platelets
- Biochemistry: glucose, sodium, potassium, calcium, inorganic phosphate, creatinine, aspartate aminotransferase (AST), alanine aminotransferase (ALT), alkaline phosphatase (AP), lactate dehydrogenase (LDH), total bilirubin (if elevated provide direct bilirubin), urea, total protein, albumin, uric acid

- Coagulation: activated partial thromboplastic time (aPTT), prothrombin time (PT)/international normalized ratio (INR)
- Urine: potential of hydrogen (pH), glucose, erythrocytes, leukocytes, protein, nitrite and glomerular filtration rate (GFR)

All safety laboratory measurements will be performed at all scheduled visits by a central laboratory (except serology which is evaluated at screening only) . Investigators will get guidance and instructions on laboratory sampling and processing through a separate Lab Manual provided by the central laboratory.

The investigator is responsible for determining and documenting if out of range laboratory values are clinically significant or not. All clinically significant values will be recorded as AEs in the eCRF and followed until resolution. Once resolved, the AE eCRF page(s) will be updated.

Continuous biochemistry, hematology, and coagulation assessments will be summarized by visit and changes from baseline using quantitative summary statistics. The data for biochemistry and hematology will also be presented in listings.

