Serology and urinalysis will be listed with collection information, and clinically significant findings, but no tabular summaries will be produced.

All laboratory values will be presented using conventional units.

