- Presence of Hemorrhage in the PED (including area of the hemorrhage) as measured by FP/FA
- Presence of Disciform Scar/Retinal Fibrosis as measured by FP/FA

18. Interim Analyses

Continuous data monitoring will be performed. One interim analysis will be performed when two-thirds of all entered subjects have reached Day 15 (Visit 4). The interim analysis will include only a subset of the secondary endpoint (i.e., accumulated AE information).

Recruitment into the trial will be stopped if the interim analysis shows relevant safety problems with ALK4290. No formal futility analysis will be conducted.

19. Pharmacokinetic Analysis

A separate PK plan will be created to describe details pertinent to the analysis of collected PK data.

20. Biomarker Analysis

A separate biomarker plan will be created to describe details pertinent to the exploratory analysis of collected biomarker data.

21. Changes from Protocol-Stated Analyses

Not applicable.

22. References

Not applicable.

23. Revision History

Documentation of revision to the SAP will commence after approval of the Final version 1.0.

24. Tables

Tables that will be included in the topline delivery are shown in boldface font and the tables, listings, and figures for the interim analyses are italicized.

Table Number	Title	Set
14.1.1	Subject Disposition	All Patients
14.1.2	Demographics and Baseline Characteristics	ITT Set
14.1.3.1	Ocular Medical History	ITT Set
14.1.3.2	Non-Ocular Medical History	ITT Set
14.1.4.1	Ocular Concomitant Medications	ITT Set
14.1.4.2	Non-Ocular Concomitant Medications	ITT Set
14.1.5	Compliance with Study Drug	Safety Set
14.1.6	Exposure to Study Drug	Safety Set
Primary and Exploratory Efficacy Analyses		
14.2.1.1	Summary of Study Eye BCVA Letter Score and Change from Baseline at Scheduled Visits	Evaluable Set
14.2.1.2	Summary of Study Eye BCVA Letter Score and Change from Baseline at Scheduled Visits	PP Set
14.2.1.3	Categorical Summary of Study Eye BCVA Letter Score Change from Baseline at Scheduled Visits	Evaluable Set
14.2.2.1	Summary of Study Eye Central Subfield Thickness (µm) and Change from Baseline as Measured by SD-OCT at Scheduled Visits	Evaluable Set
14.2.2.2	Summary of Study Eye Central Subfield Thickness (µm) and Change from Baseline as Measured by SD-OCT at Scheduled Visits	PP Set

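### The protocol promises tabulated categorical safety data, but the SAP gives qualitative urinalysis a listing only and does not declare the departure, so urine shifts not judged clinically significant appear in no table

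*Protocol*

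**What the plan says.** Protocol 10.4.2 includes among the safety endpoints "Changes from baseline in clinical laboratory values" and sets the reporting format for qualitative data: "Tabulations of frequencies/proportions will be used for the evaluation of categorical (qualitative) data".

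Protocol 7.2.2 defines the panels: "Safety laboratory examinations will include hematology, biochemistry, coagulation and qualitative urine analysis". It gives the urine analytes as "Urine: potential of hydrogen (pH), glucose, erythrocytes, leukocytes, protein, nitrite" and has urine taken at every visit.

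SAP section 16 opens with a general commitment: "Other safety endpoints including slit-lamp biomicroscopy, IOP, clinical laboratory values, physical examination, and vital signs will be summarized using descriptive statistics". It makes no exception there for urine. SAP 16.4 then separates the panels. For three of them, "Continuous biochemistry, hematology, and coagulation assessments will be summarized by visit and changes from baseline using quantitative summary statistics". For urine, "Serology and urinalysis will be listed with collection information, and clinically significant findings, but no tabular summaries will be produced".

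The table list in SAP section 24 agrees with 16.4. It has summary and shift tables for biochemistry, coagulation and hematology (14.3.10.1.1 to 14.3.10.3.2) and none for urine. Urine appears only as Listing 16.2.8.8. The entry under "21. Changes from Protocol-Stated Analyses" is that none apply.

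**The concern.** Dipstick protein, erythrocytes, leukocytes, glucose and nitrite are categorical safety laboratory data, so they fall under the protocol's tabulation sentence. The SAP withdraws the table for this panel without giving a reason or recording the change.

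The practical consequence concerns low-grade findings. In an open-label, single-arm study at up to 12 sites, whether a new trace or positive result is clinically significant is decided case by case by the investigator. Several subjects could each move from negative to positive, with each result judged not significant. A shift table is built to show that pattern, and adverse event tables would miss it. Safety is the only secondary endpoint, and subjects with calculated GFR down to 30 mL/min may enrol, so urine protein and erythrocytes are worth summarizing when they are already collected.

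**Working it through.** The plan states no figure for this point, so there is none to reproduce. The check compares the texts, traces how a urine result can reach a table, and counts results for scale.

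**1. Is urinalysis within the protocol's commitment?** Yes. Protocol 7.2.2 calls it a safety laboratory examination and calls it qualitative. Protocol 10.4.2 covers both laboratory change and the tabulation of qualitative data.

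**2. Does the SAP deliver it?** No. SAP 16.4 rules out a table, and section 24 contains none. The general statement in SAP section 16 says that laboratory values will be summarized. Its qualifier about appropriateness applies to changes and shifts, not to the summary itself.

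**3. Is the departure declared?** No. SAP section 1 says that SAP methods supersede protocol methods, so the rule that governs is clear. Section 21 nevertheless reports no change.

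**4. By what route can a new urine positive be counted?**
- Judged clinically significant: recorded as an adverse event (Protocol 7.2.2, SAP 16.4). It is treatment-emergent if it starts or worsens on or after first dose, and is then counted as number and percentage of subjects by system organ class and preferred term (SAP 16.1).
- Not judged clinically significant: it appears in no table. It may appear in Listing 16.2.8.8, but the wording of SAP 16.4 leaves open whether that listing shows every dipstick value or only collection information and clinically significant findings.

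**5. Could a shift be computed from the planned data?** Yes. Laboratory tests are scheduled at Visits 1 and 2, so a baseline exists under SAP 9.2, and again at Visits 3 to 10.

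**6. Scale.** Inputs: 30 subjects (Protocol 10.5); on-treatment post-baseline visits 3 to 8, which is 6 (schedule of events); 2 analytes, protein and erythrocytes.
- Samples: 30 x 6 = 180.
- Protein and erythrocyte results: 180 x 2 = 360.

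This is an upper bound at full attendance. It counts results that enter no laboratory table, not abnormal results. The documents give no expected rate of new positives.

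**The case against.** The strongest case against has four parts.

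- **The events that matter are counted.** A reader might infer that new proteinuria or hematuria on drug is never counted. The documents do not support that: clinically significant results become adverse events and enter the treatment-emergent tables. This part of the objection stands and limits the point to results below that threshold.
- **The SAP governs and is explicit.** Protocol 10.1 leaves analytical detail to the SAP, and the SAP claims precedence, so no analyst faces two instructions. That is correct. It does not make the entry in section 21 accurate, and it does not supply the summary that the protocol describes.
- **Renal safety does not rest on dipsticks.** Creatinine, urea, albumin and total protein sit in the biochemistry panel, which has summary and shift tables. The adverse events of special interest include no renal event, and the renal risk named in Protocol 2.3.1 is attributed to fluorescein angiography, not to the drug. This stands and keeps the severity low.
- **The panel is small and hard to interpret.** With about 30 subjects, a complete listing can be read by hand; without a control arm, low-grade changes are hard to attribute to the drug. Both are fair, but the first depends on the listing being complete, which SAP 16.4 does not make clear.

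A reader might also size the gap as 5 analytes x 30 subjects x 8 post-baseline visits = 1,200 results. That count includes Visits 9 and 10, which follow the end of treatment, and three analytes that bear on neither proteinuria nor hematuria.

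Physical examination is a parallel case. Protocol 10.4.2 names change from baseline, while SAP 16.7 lists only whether the examination was done. If section 21 is revised, both belong there.

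**Conclusion.** The point holds in a limited form. The protocol commits to tabulating categorical safety data and to laboratory change from baseline; the SAP gives qualitative urinalysis a listing only and does not declare the departure. Shifts in urine protein or erythrocytes that are not judged clinically significant appear in no table, which covers at most 360 on-treatment results.

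That bound assumes 30 subjects, full attendance at Visits 3 to 8, and two analytes. No estimate of how many would be new positives is possible from the documents. The primary analysis and the adverse event tables are unaffected. This is a low-cost improvement to the safety reporting and a correction to the record of changes.

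**What to change.** In SAP 16.4 and section 24, add one urinalysis shift table on the Safety set: baseline category against the category at each visit and against the worst post-baseline category, with counts and percentages, for protein, erythrocytes, leukocytes, glucose and nitrite. Neither document defines dipstick categories, so specify that the central laboratory's reported categories are used and state their order, so that the worst category is defined in advance. Keep serology listed only, since the SAP schedules it at screening alone. State that Listing 16.2.8.8 shows all urine results.

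If the sponsor prefers listing only, enter that in SAP section 21 with a reason, and still state that the listing is complete.

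The cost is one extra safety table. It needs no new data collection, because SAP section 7 already provides for transfer of the external safety laboratory data for analysis.

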### 10.4.3 EXPLORATORY ANALYSES

Observed values as well as changes from baseline in CST, IRF, SRF, and PED as measured by SD-OCT and fundus photography/FA will be summarized using descriptive statistics. Pharmacokinetic, biomarker, and pharmacogenomic analyses will be carried out using an exploratory approach to investigate the potential influence on the therapeutic response of ALK4290.

**10.4.4 PLANNED INTERIM ANALYSES**

Continuous data monitoring will be performed. One interim analysis will be performed when 2/3 of all entered subjects have reached Day 15 (Visit 4). It will include only the primary and a subset of the secondary endpoints, (i.e., mean change in BCVA as measured by ETDRS and the accumulated AE information). Recruitment into the trial will be stopped if the interim analysis shows relevant safety problems with ALK4290. No formal futility analysis will be conducted.

**10.5 SAMPLE SIZE**

A total of 30 subjects will be enrolled in the study with the intent of obtaining ~25 evaluable subjects who have completed at least 3 weeks of treatment and evaluations through Visit 4. Subjects who discontinue prior to Visit 4 may be replaced. Subjects who withdraw or are withdrawn during screening will be replaced. The study is not powered for detecting statistically significant differences in therapeutic parameters in subjects with wAMD receiving ALK4290. However, the proposed sample size may be sufficient to identify trends in the effects of ALK4290 and in the relationship between dose and response.

**11 SOURCE DOCUMENTS AND ACCESS TO SOURCE DATA/DOCUMENTS**

Each participating site will maintain appropriate medical and research records for this trial, in compliance with ICH E6 R2 and regulatory and institutional requirements for the protection of confidentiality of participants. Each site will permit authorized representatives of regulatory agencies, the IRB/IEC, the sponsor, or the sponsor’s representatives to examine (and when permitted by applicable law, to copy) clinical records for the purposes of quality assurance reviews, audits, and evaluation of the study safety, progress, and data validity.

Source data are all information, original records of clinical findings, observations, or other activities in a clinical trial necessary for the reconstruction and evaluation of the trial. Examples of these original documents and data records include, but are not limited to, hospital records, clinical and office charts, laboratory notes, memoranda, participant’s memory aids or evaluation checklists, pharmacy dispensing records, recorded audio tapes of counseling sessions, recorded data from automated instruments, copies or transcriptions certified after verification as being accurate and complete, microfiches, photographic negatives, microfilm or magnetic media, x-rays, and participant files and records kept at the pharmacy, at the laboratories, and medico-technical departments involved in the clinical trial.

It is not acceptable for the eCRF to be the only record of a subject’s participation in the study. This is to ensure that anyone who would access the medical record has adequate knowledge that the subject is participating in a clinical trial. Source document templates will be developed for this study.

